#### Feasibility and Baseline Demographics

Data will be reported as mean (standard deviation) for continuous variables, and number (percentage) for nominal data. Differences between the intervention and control groups will be analysed within population group (HC/AzD/MCI) using Chi-Square for nominal data, and independent t-testing for continuous data. Any differences between population groups will also be reported.

#### Outcome Data

The difference for each participant between baseline and follow-up assessment for each of the continuous outcome measures described in Section 6.2 (secondary outcome measures) will be reported along with the overall mean difference. To assess the impact of the intervention and population group on each of these differences, a two-way ANOVA will be carried out. The interaction between population group and treatment group will also be included to assess if the difference between the treatment groups is different between the population groups.

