## 6. STUDY DESIGN

### 6.1 Summary of Trial Design

This is a prospective, feasibility, RCT of CT in healthy older adults, and adults with AzD, MCI, or post-ischaemic stroke. This trial is un-blinded, due to the nature of the intervention. The expected duration of participation per individual is three to six months. Initially, participants will be approached by a member of the clinical care team or research support staff, who will screen and identify eligible participants. Study specific information will then be provided by the researcher. Following this, participants will undergo informed consent. Each participant will have two visits (initial and follow-up assessment). After the first visit, participants will be randomised to control or intervention (CT), and will complete an 8-12 week CT program, if selected for the intervention group. Participants will be randomised using Sealed Envelope ©, an online, commercially available randomisation tool. At the end of the trial, participants will be given the option to participate in a qualitative study by semi-structured interviews or focus group. A flow chart for this process can be seen in Appendix A.

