## 6.2 Primary and Secondary Endpoints/Outcome Measures

Primary end point measures:

- 1) Number of participants successfully recruited
- 2) Percentage of participants able to successfully complete the CT program and all assessments
- 3) Percentage of participants with full bilateral data for CBFv
- 4) Feasibility of randomisation to waiting list control

Secondary end points:

- 1) Change in cognition score as detected by the Addenbrooke's cognitive examination (ACE-III)
- 2) Change in functional status - Lawton IADL
- 3) Change in mood – GDS-15
- 4) Change in quality of life measure – DEMQOL
- 5) Change in task activation increase in CBFv from baseline

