#### 8.4 Baseline Assessments

Participants who meet the inclusion criteria, will undergo baseline assessments with a member of the research team, or research delivery officer, either at home, designated LPT research space, or invited to attend the CHiASM research space. The first visit will take place at the CHiASM research space, based at the Leicester Royal Infirmary, for an assessment of cognition (ACE-III) and neurovascular function (outline below). Approximately 20-25% of potential participants will have insufficient bilateral temporal windows for assessment, and this would preclude their study entry. Following successful window insonation, and completion of the neurovascular assessment, the following baseline assessments will be undertaken at the same visit or within two weeks at the participant's home: mood (GDS-15), function/ADLs (Lawton-IADL), quality of life (DEMQOL), handedness (Edinburgh handedness inventory).

An assessment of neurovascular function will take place using a protocol validated by this group previously (35). Participants will be asked to refrain from caffeine, nicotine, alcohol, heavy meals, or strenuous exercise for at least four hours prior to the neurovascular assessment. In summary, participants will undergo continuous beat-to-beat monitoring of cerebral blood flow velocity (CBFv) using transcranial Doppler ultrasound (TCD, DWL Doppler box), blood pressure (Finometer), heart rate (3-lead ECG), and end-tidal CO2 (ETCO2, capnography, nasal speculum). Participants will undergo a five-minute baseline recording. Participants will be asked five selected tasks from the ACE-III (attention, memory, language, fluency and visuospatial domains) to stimulate changes in CBFv, which can be measured by the above methods.

For the post-stroke sub-group, a further four tasks will be undertaken. The serial sevens will be completed in addition to serial 2s and 17s, and the naming words with “p” will be completed in addition to words beginning with “r” and “v”. This is to identify subtler deficits that may be present in the stroke sub-group.

Data collected on baseline demographic information will include the following:

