#### 8.5 Randomisation and Codebreaking (if applicable)

Randomisation will be performed using Sealed Envelope®, by the researcher. This is an online-based randomisation tool which uses random permuted blocks to allocate participants to waiting list control or intervention. Participants will be enrolled and assigned a PIN consecutively, and randomised to a treatment arm corresponding to the PIN. Given the nature of the trial, it is not possible to blind participants to the intervention. The Investigator will be providing weekly telephone support with the intervention, in addition to undertaking baseline and follow-up measurements, and therefore blinding of the investigator is also not possible. However, data analysis will be blinded by generating a batch-anonymised data set. Randomisation will be undertaken at the initial visit. As this is an un-blinded trial, code breaking will not be required.

Once participants have been randomised to the intervention arm, they will be provided with information on how to access and use the CT program.

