#### 8.6 Subsequent Assessments

Participants randomised to the intervention will be followed-up on a weekly basis by the investigator with a telephone call to troubleshoot any problems arising with software/cognitive training program, or any changes in circumstance that would preclude ongoing study involvement. Participants will be followed up after 8-12 weeks of cognitive training, and will return to the CHIASM laboratory to repeat the baseline assessments (cognition (ACE-III), mood (GDS-15), function/ADLs (Lawton-IADL), quality of life (DEMQOL), neurovascular function (TCD), blood pressure (Finometer), heart rate (3 lead ECG) and end-tidal CO2 (ETCO2, capnography, nasal speculum). Adverse events will also be assessed at this time point.

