## 11. STATISTICS

### 11.1 Description of Statistical Methods

All data will be tested for normality prior to statistical testing using Shapiro-Wilks or visual inspection of histograms. Where data are found to be non-parametric, data will be appropriately transformed prior to statistical testing, and parametric tests then applied. Data will be recorded in Microsoft Excel. Statistical analyses will be performed using the latest version of SPSS for Windows, and graphs will be produced using the latest version of GraphPad Prism for Windows.

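### Secondary outcomes are analysed as raw change scores with no baseline covariate: a minor, conditional loss of precision that data already collected could recover

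*Combined protocol and SAP*

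**What the plan says.** Under Outcome Data, Section 11.1 forms each participant's difference between the two visits for every continuous secondary outcome. It then specifies: "To assess the impact of the intervention and population group on each of these differences, a two-way ANOVA will be carried out". The arm-by-population interaction is added. No baseline value or other covariate appears in the model, and the rest of the document does not mention baseline adjustment.

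Every secondary outcome is measured at both visits. Section 8.4 collects them at baseline, and Section 8.6 says participants "will return to the CHIASM laboratory to repeat the baseline assessments". Appendix C agrees.

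Three other places bear on whether the baseline value can serve as a covariate:

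- **Timing.** Section 8.5 says "Randomisation will be undertaken at the initial visit", while Section 6.1 places randomisation after that visit. Once the neurovascular assessment is complete, Section 8.4 says "the following baseline assessments will be undertaken at the same visit or within two weeks" at home. This covers GDS-15, Lawton-IADL and DEMQOL. Appendix C gives these three a one-month baseline window.
- **CBFv endpoint.** Section 6.2 lists "Change in task activation increase in CBFv from baseline". Section 8.4 also uses the word baseline for the resting trace: "Participants will undergo a five-minute baseline recording".
- **Use of the results.** Section 11.1 (Power calculation) will size a larger trial from these outcome data, without saying which SD will be used.

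**The concern.** A change score uses the baseline value but forces its coefficient to be 1. If the within-group slope of follow-up on baseline is below 1, as regression to the mean makes likely, the change score over-corrects and carries avoidable noise. With about 10 participants per arm in each population (assuming 1:1 allocation and no losses), chance baseline differences between arms will be common, and the plan does not say how they would be handled.

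Three things are at stake. The arm and interaction estimates for the secondary outcomes may be less precise than the data allow. The main-trial sample size may rest on an SD that does not match that trial's analysis. And since neither participants nor the investigator taking the measurements is blinded, three of the baselines may be recorded with allocation known. That would affect the planned change score and an adjusted model alike.

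**Working it through.** **Inputs.** The synopsis plans 80 participants (4 × 20) and Section 11.2 plans 60 (3 × 20), so both were used. There is no power-based figure to reproduce, because Section 11.2 states that no formal power calculation was done. Assumed, because the documents do not give them: r, the within-group baseline/follow-up correlation; k, baseline SD divided by follow-up SD; 1:1 allocation in equal cells; and normal data.

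**Formula.** With follow-up SD set to 1, the change-score variance is 1 + k² − 2rk and the baseline-adjusted variance is 1 − r². Estimating one slope costs a factor (v − 1)/(v − 2), where v is the residual df before the covariate is added. Hence

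ratio (change / adjusted) = [1 + (k − r)²/(1 − r²)] × (v − 2)/(v − 1).

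With k = 1 the bracket is 2/(1 + r). For 80 analysed, v = 80 − 8 = 72 and the df factor is 70/71 = 0.986. For 60, v = 60 − 6 = 54 and the factor is 52/53 = 0.981. For example, at r = 0.7 with 80 analysed: 2/1.7 × 0.986 = 1.16.

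| Case | r = 0.5 | 0.7 | 0.8 | 0.9 |
|---|---|---|---|---|
| k = 1, 80 analysed | 1.31 | 1.16 | 1.10 | 1.04 |
| k = 1, 60 analysed | 1.31 | 1.15 | 1.09 | 1.03 |
| k = 1, 48 analysed (60 less 20%) | 1.30 | 1.15 | 1.08 | 1.03 |
| k = 0.8, 80 analysed | 1.10 | 1.01 | 0.99 | 1.04 |
| k = 1.25, 80 analysed | 1.73 | 1.57 | 1.54 | 1.62 |

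Confidence-interval width goes with the square root. The first row gives intervals about 15%, 8%, 5% and 2% wider.

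**Where the gain vanishes.** This happens when the slope r/k is close to 1. With equal SDs it needs r above 0.97 (80 analysed) or 0.96 (60). At k = 0.8 it happens for r between 0.72 and 0.86 (80) or 0.70 and 0.87 (60). Under a common slope, the most that adjustment can then cost is the df factor: 71/70 − 1 = 1.4% of variance with 80, and 53/52 − 1 = 1.9% with 60.

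**Unequal slopes.** Suppose r is 0.5, 0.6, 0.8 and 0.9 in the four populations, with equal SDs and one common slope. The pooled slope is 0.7. The residual variance about it is 1 + 0.49 − 1.4r, against 2(1 − r) for the change score. At r = 0.9 this is 0.23 against 0.20, a ratio of 0.87; at r = 0.5 it is 0.79 against 1.00, a ratio of 1.27. In simulation, which includes the cost of estimating the slope, the ratio was about 1.16 overall and about 1.25, 1.22, 1.06 and 0.85 by population. The population with r = 0.9 therefore loses precision. With a separate slope per population, its ratio would be 2/1.9 × 16/17 = 0.99.

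**Baseline recorded after allocation.** Suppose knowledge of allocation shifts one arm's recorded baseline by 0.10 SD and nothing else. With equal SDs the change-score arm effect is biased by 0.10 SD. The adjusted effect is biased by 0.10 × slope: 0.05, 0.07, 0.08 and 0.09 SD at the four values of r. Simulation agrees.

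**Consequence for the larger trial.** For an assumed effect of 0.5 SD at 80% power and two-sided 5%, the number per arm using the change-score SD against the adjusted SD is 63 against 48 at r = 0.5, 38 against 33 at r = 0.7, and 13 against 12 at r = 0.9.

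**The case against.** The strongest reply is that a change-score ANOVA is a legitimate pre-specified analysis. The outcomes are secondary, the trial is a feasibility study with no precision target, and an adjusted analysis could be added later from stored data. All of that stands, and it is why the point goes no higher than minor.

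The size of the loss is also unknown. The range 0.99 to 1.73 reflects the values of r and k tried: at r = 0.3 the same formula gives 1.52 with equal SDs and 1.96 at k = 1.25. Only a conditional statement is supported.

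A common slope can hurt a particular population, and the plan specifically wants the arm-by-population comparison. Equal slopes and SDs are doubtful across healthy controls, MCI, Alzheimer's disease and stroke. If one population had r = 0.9 and an SD of only 0.4 (the others having r = 0.8, 0.6, 0.5 and SDs 0.7, 1, 1), simulation puts its ratio near 0.7 while the overall ratio stays about 1.21. This stands as a reason to examine slopes by population. It does not favour fixing every slope at 1.

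The timing conflict is not caused by the missing covariate, and it biases the change score more than the adjusted estimate. It belongs here because a covariate must precede knowledge of allocation to be safe. On the CBFv endpoint, Sections 5.2 and 11.1 make the visit-to-visit comparison fairly clear, so only a clarifying sentence is needed.

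**Conclusion.** The concern holds as a minor point about efficiency. The planned analysis is not invalid, and no primary feasibility endpoint depends on it. With equal SDs and r between 0.5 and 0.9, intervals for the secondary outcomes would be about 2% to 15% wider than necessary with 80 analysed, and much the same with 60. Where the slope is close to 1 there is no gain, and a common-slope adjustment costs at most about 1.4% (80) or 1.9% (60) of variance. Where slopes differ between populations, the overall estimate still gains in the cases examined, but an individual population can lose.

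Confidence is high that the covariate is absent and that the data for it are collected. The size rests on the assumed r and k, which the documents do not supply. For GDS-15, Lawton-IADL and DEMQOL, freedom from bias is not established under either analysis until the order of baseline assessment and randomisation is settled. The choice of SD for the power calculation is a reporting matter, since both SDs can be computed from the data.

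**What to change.** In Section 11.1:

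- Add the baseline value of the same outcome as a covariate to the model with arm, population and their interaction, and report adjusted differences with 95% confidence intervals.
- Fit baseline-by-population slopes as a sensitivity analysis, and consult it before interpreting population-specific contrasts.
- Section 11.1 also provides that "Where data are found to be non-parametric, data will be appropriately transformed prior to statistical testing". If this is used, apply the same transformation to the values at both visits.
- For the CBFv endpoint, state that the covariate is the task-activation response for the same task and side at the baseline visit, not the resting recording.
- Report the residual SD and the within-group baseline/follow-up correlation with its confidence interval, and state that the power calculation will use the SD that matches the larger trial's planned analysis.

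In Section 8.5, state that baselines must be recorded before allocation is known. Reconcile Sections 6.1, 8.4 and 8.5 and the one-month window in Appendix C by randomising only after GDS-15, Lawton-IADL and DEMQOL are complete. Report how many baselines were nevertheless taken after allocation.

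The cost is 1 df in a model SPSS already fits, no new data, and a few sentences. Waiting for home questionnaires could delay allocation by up to two weeks for some participants, and this must still fit the four to six weeks from screening to randomisation in Section 8.1.

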### 5.2 Secondary Objectives

- 1) Are there any clinical benefits of a brain training program in patients with dementia and any difference between groups (MCI/AzD/healthy older adults/post-ischaemic stroke) in ability to carry out everyday activities, memory, mood, and quality of life outcomes?
- 2) Are there any changes in blood flow responses to cognitive tasks using TCD before and after brain training?
- 3) Are there any brain blood flow markers that can be used to predict who will benefit from brain training, and in which memory areas to generate a personalised training plan for individual patients?

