### 7.2 Inclusion Criteria

Study specific inclusion criteria will be as follows:

One of:

- 1) Healthy controls will be free of any medical co-morbidity or medication that could adversely affect cognition. Volunteers with well-controlled co-morbidities (i.e. hypertension, diabetes, will be considered for inclusion)
- 2) MCI as defined by NIA/AA 2011 and Petersen criteria
- 3) AzD as defined by the NIA/AA 2011 criteria
- 4) Ischaemic stroke within the last 12 months

And:

- 5) Deficits will be mild to moderate as defined by Montreal Cognitive Assessment (MoCA) score of  $>/=9$  for all participants with MCI or Alzheimer's disease (32-34).
- 6) Willing to participate
- 7) Capacity to consent to the study/personal consultee
- 8) Patients on and off anti-dementia medications will be included (acetylcholinesterase inhibitors, glutamate receptor antagonists)
- 9) Good understanding of written and spoken English
- 10) Age  $>50$  years (MCI, AzD, and healthy controls only)
- 11) Access to the internet and a computer or laptop.

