### 7.3 Exclusion Criteria

Study specific exclusion criteria as follows:

- 1) Healthy controls with any medical co-morbidity or medication that could adversely affect cognition, or poorly controlled medical co-morbidities (i.e. hypertension, diabetes)
- 2) Unwilling to take part
- 3) Unable to consent/no personal consultee
- 4) Major medical co-morbidity; severe heart failure (ejection fraction <20%), significant carotid artery stenosis >50%), severe respiratory disease, major stroke (MCI and AzD groups only)
- 5) Pregnancy, planning pregnancy, or lactating
- 6) Inadequate bilateral TCD windows
- 7) Participants already enrolled into other interventional studies
- 8) Insufficient understanding of written and spoken English
- 9) Age <50 years (MCI, AzD, and healthy controls only)
- 10) No access to the internet and a computer or laptop.

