##### Demographics

The age, sex, ethnicity, smoking status, alcohol intake, height, weight, BMI, years of education, and socioeconomic status (postcode) will be recorded.

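### Population group is not randomised, yet its effect on change scores is tested with no adjustment for age, sex or education, so the population contrasts may partly reflect those variables

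*Combined protocol and SAP*

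**What the plan says.** Under Outcome Data, section 11.1 takes as its outcome "The difference for each participant between baseline and follow-up assessment for each of the continuous outcome measures" and states that "a two-way ANOVA will be carried out". The purpose given is "To assess the impact of the intervention and population group on each of these differences", and "The interaction between population group and treatment group will also be included". No covariate is named there or elsewhere in section 11. Section 11.3 sets significance at p<0.05.

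The population comparison is a stated aim: secondary objective 1 in section 5.2 asks for "any difference between groups (MCI/AzD/healthy older adults/post-ischaemic stroke").

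Section 8.5 randomises participants to training or waiting list only. Population is fixed by diagnosis under section 7.2, where the lower age limit carries the restriction "years (MCI, AzD, and healthy controls only"). Section 7.3 mirrors it: "Age <50 years (MCI, AzD, and healthy controls only"). Stroke participants have no age limit.

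Section 8.4 (Demographics) says: "The age, sex, ethnicity, smoking status, alcohol intake, height, weight, BMI, years of education, and socioeconomic status (postcode) will be recorded". The only use planned for these variables is descriptive. Under Feasibility and Baseline Demographics, section 11.1 says that differences between population groups will be reported.

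**The concern.** The model treats arm and population alike, as factors whose *impact* is to be assessed. Randomisation supports that word for arm but not for population. Section 8.1 recruits healthy volunteers through posters, a university volunteer list, and patients' friends, family and carers. Patients with MCI or AzD come mainly from memory and geriatric services, GP database searches and community groups. Stroke participants come from stroke and rehabilitation wards, stroke and TIA clinics, and existing departmental studies. The routes overlap in part, but nothing makes the groups alike in age, sex or education, and the age rule differs for stroke.

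At stake is the reading of secondary objective 1. If one of these variables affects decline, practice effect, response to training or task-evoked blood flow over the study period, a difference between populations could be produced or hidden by it and then be reported as a feature of the disease.

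**Working it through.** The plan has no figure of its own to reproduce, because section 11.2 says that no power calculation was done. The check asks how far the false-positive rate of a population test can move from 5% when there is no true population effect.

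**Inputs from the documents.** Four populations of 20 (synopsis), two arms, alpha 0.05 (section 11.3). Error degrees of freedom: 80 − 4 × 2 = 72, if stroke is in the model and all 80 have data.

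**Assumptions not in the documents.** The age gap between populations and the relation of age to change. Age stands in for all three variables; no figure is offered for sex or education.

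**1. One 20 v 20 contrast.** Within-group SD of change is set to 1.
- Bias = correlation of age with change × age gap in SD units.
- Squared standard error = 2/20 = 0.1, so noncentrality = bias² / 0.1, referred to F(1, 72).

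| Correlation | Age gap (SD) | Bias (SD) | Noncentrality | False-positive rate |
|---|---|---|---|---|
| 0.1 | 0.5 | 0.05 | 0.025 | 0.053 |
| 0.2 | 1.0 | 0.20 | 0.40 | 0.096 |
| 0.2 | 1.25 | 0.25 | 0.625 | 0.122 |
| 0.4 | 1.0 | 0.40 | 1.60 | 0.239 |
| 0.4 | 1.25 | 0.50 | 2.50 | 0.345 |

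**2. The planned four-group F test, with age in years.** Assume a within-group age SD of 8 years, a stroke group younger by D years, and a slope of b residual SDs of change per 10 years of age.
- Shift in the stroke mean = b × D/10.
- Variance within groups = 1 + (0.8b)².
- Noncentrality = 20 × 0.75 × shift² / variance, on F(3, 72).

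Example: D = 15 and b = 0.3 give a shift of 0.45 and a variance of 1 + 0.24² = 1.0576. Noncentrality is 20 × 0.75 × 0.2025 / 1.0576 = 2.87, and the false-positive rate is 0.25.

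| Stroke younger by | b = 0.1 | b = 0.3 | b = 0.5 |
|---|---|---|---|
| 10 years | 0.06 | 0.13 | 0.28 |
| 15 years | 0.07 | 0.25 | 0.58 |
| 20 years | 0.09 | 0.43 | 0.85 |

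If ages are equal or b = 0, the rate is 0.05. In simulations (4,000 runs per scenario; D from 0 to 20 years, b = 0.3 or 0.5), adding age as a covariate gave 0.048 to 0.055 throughout.

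**3. The interaction.** Suppose age changes the training response, so that the trained arm gains b per unit of age and the control arm does not. The arm difference in a population with mean age A is then b × A, and two populations differ in it by b × (A₁ − A₂). An additive age term has the same coefficient c in both arms. With ages balanced by randomisation within a population, it contributes cA − cA = 0 to the arm difference and so removes nothing. An age-by-arm term is needed. In simulation with D from 10 to 20 years, the unadjusted interaction test rejected at 0.07 to 0.13 (b = 0.3) and 0.11 to 0.29 (b = 0.5). With age and age-by-arm in the model, across D from 0 to 20 years, it rejected at 0.046 to 0.057.

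**4. Is stroke in the model?** The synopsis and sections 5.2 and 7.1 include stroke, and section 11.7 analyses all randomised participants. The group list under Feasibility and Baseline Demographics in section 11.1 names only HC/AzD/MCI, and section 11.2 plans three sub-groups totalling 60. Read literally, section 11 would have 60 − 3 × 2 = 54 error degrees of freedom and one age rule for all groups.

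**The case against.** The strongest reply is that the outcome is change within a person. Any stable effect of age, sex or education on the level of cognition, function or mood cancels. Confounding requires these variables to affect change over 8-12 weeks or the response to training. This stands, and it limits the point.

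Second, the sizes rest wholly on assumptions. A reader might infer that, because stroke has no age limit, the stroke group will be younger and a false disease effect is to be expected. The documents do not support that: lifting a lower limit permits younger participants but does not show that they will be recruited, and no age data are given. The mildest case above is effectively nominal.

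Third, baseline differences between populations will be reported, so a reader could see an imbalance. That is disclosure; it does not adjust the outcome contrast.

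Fourth, if section 11 means three populations, the argument from the age rule falls away. What remains is the difference in recruitment routes, with a shared lower age bound that does not by itself equalise ages above it.

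Fifth, this is a feasibility trial and the contrasts are secondary. That lowers the priority. It does not remove the point, because the plan still tests these contrasts at p<0.05 and describes them as impact.

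**Conclusion.** The point holds in a limited form. The population main effect is a non-randomised comparison tested without adjustment, although age, sex and years of education are already collected. The population-by-arm interaction is open to the same misreading if age modifies the training response. A reader might go further and infer that the treatment effect is biased. It is not: arm is randomised, and the comparison of arms within a population is unaffected.

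For a 20 v 20 contrast, the false-positive rate ranges from about 5% (correlation 0.1, gap 0.5 SD) to 10-35% (correlation 0.2-0.4, gap 1-1.25 SD). The higher values in the second table need larger gaps or steeper slopes still. All are illustrations for age alone, with 80 complete participants and stroke in the model; none is a forecast for this trial. The priority is moderate: secondary analyses of a feasibility study, with an inexpensive remedy.

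**What to change.** In section 11:

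- State whether the post-stroke group is in the ANOVA, and reconcile sections 11.1 and 11.2 with the synopsis and sections 5.2 and 11.7.
- For population contrasts, report unadjusted estimates and estimates adjusted for age, sex and years of education, each with a 95% CI.
- For the population-by-arm interaction, add a sensitivity model that also contains age-by-arm, since main-effect covariates alone do not correct it.
- Replace *impact* with *association* for population group, and label these contrasts exploratory.
- State that adjustment depends on overlap in age between the groups.

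The cost is wording, using data already collected. The adjusted main-effect model spends about three error degrees of freedom (72 to 69 with four populations). The interaction sensitivity model spends four or more (68 or fewer), with about 10 participants per cell if arms are balanced. Where age overlap is poor, the adjusted estimates rely on the assumed linear age effect, which is why the unadjusted estimates should stand beside them.
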